# **10.3** SIGNS AND SYMPTOMS

Summary tables (number and % patients) grouped by System Organ Class (SOC) will be presented by DL and overall for Signs and Symptoms present at baseline (i.e., concomitant diseases "Ongoing" at the screening visit) and for Medical History (i.e., events "Not Ongoing" at the inclusion visit).

The totals of each Signs and Symptoms and the number of patients with at least one Sign and/or Symptom will be tabulated for the safety population for baseline Signs and Symptoms and for Medical History.

### **10.4** CONCOMITANT MEDICATIONS

Summary tables (number and % of patients) grouped by the first and the last level of ATC code will be presented by DL and overall. Concomitant medications are those ongoing at or started after the first treatment.

Presence at baseline of selected concomitant medications classes (e.g. cardiac antiarrhythmics, antihypertensive drugs, neurologic and/or psychiatric drugs) will be described by DL and overall.

# **10.5** MEASUREMENTS OF COMPLIANCE

Compliance to the study treatment will be derived only for patients with no missing data (collected in the CRF) using the following definition:

Compliance (%) = [nb dose not equal to 0 in the CRF / ( (nb completed lines in the CRF + 1 )] \* 100

Compliance over the whole study treatment period (from first visit to last visit) and over cycle 1 only will be calculated.

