5.2.3 Schedule

Details of the exact dose and time of administration of medication (day/month/year, h: min) will be documented in a specific patient's diary (Appendix VII; section 16.7) and reported in the case report form.

- Study medication: OTX015/MK-8628. All patients enrolled should receive first study treatment intake within 7 days after registration.
- The study treatment may be delivered to hospitalized patients or outpatients, depending of their need of supportive care according to investigator's judgment. However, for the once-a-day schedule, 3 patients by dose level (among a minimum number of patients of 6 by DL: 3

with AL and 3 with other malignancies) will be hospitalized at least 24 hours for complete PK sampling (see section 7.3.3.1) All other patients enrolled in the same DL will have limited PK sampling and will stay at least 8 hours at the hospital on day 1. For the BID schedule, all patients will be hospitalized for 24 hours for PK sampling.

- Route: Oral capsules will be swallowed with water in a fasted state before lunch, at least 3 hours after breakfast end), except the first dose (C1D1) that will be taken at the hospital before breakfast.
- Capsules must not be open or chewed.
 - Schedule: The schedule of administration will initially depend on the indication:
 patients with acute leukemia will initially take OTX015/MK-8628, over 14
 consecutive days followed by a 7-day rest period. Upon SMC decision, patients with acute leukemia will take OTX015/MK-8628 continuously without planned rest period, like patients with other haematological malignancies.

- patients with other malignancies will take OTX015/MK-8628 continuously without planned rest period

- In all cases, one cycle = 21 days by convention and day 22 = day 1 of next cycle.

ACUTE LEUKEMIA (initial schedule before amendment # 4)

4 5 6 7 8 9 10 11 12 13 14 15 19 20 21 3 16 17 18 22 etc

OTHER HEMATOLOGICAL MALIGNANCIES and ACUTE LEUKEMIA after amendment # 4

3 4 5 8 9 13 19 2 6 10 12 14 15 16 18 20 21 22 etc.

- Interruptions are planned in case of toxicity according to specific guide lines (see section 0). If study medication interruptions due to toxicity are regularly observed, the SMC may decide to modify the schedule and to assess new cohorts of patients with this modified schedule.

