### Expansion part

- Once the RD will be established with at least 3 patients having received at least 2 cycles of study treatment for each subset, the study will be prolonged with expansion cohorts in selected patients to confirm feasibility, safety, PK and PD at the RD. At least 12 evaluable patients with acute leukemia will be treated at the RD established for patients with acute leukemia. At least 12 evaluable patients with diffuse large B-cell lymphoma (DLBCL) or multiple myeloma (MM) will be treated at the RD established for patients. Additional expansion cohorts may be decided by the SMC, based upon the data collected during the dose escalation phase.
- The RD for expansion cohorts for both acute leukemia and other hematologic malignancies was established at 80 mg QD days 1 to 14 of 21-day cycles (2 weeks ON/one week OFF).

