#### Treatment compliance

Patients will record daily in a specific diary, the number of capsules swallowed, time of intake, as well as possible reactions, including vomiting, and their time of occurrence. At each study visit the hospital pharmacist of the study center will provide the patient with the needed number of capsules for the visit interval and retrieve the unused capsules that will be kept until study end for accountability by the study monitor.

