# 6. STATISTICAL METHODOLOGY

# 6.1 GENERAL CONSIDERATIONS

The statistical analysis will be performed by eXYSTAT, under the responsibility of the Sponsor OncoEthix GmbH and the study CRO, OTD, on the basis of the present document.

The statistical analysis will be performed using SAS® software, version 9.4 in a Windows XP operating system environment.

The baseline value is defined as the last available value prior to administration of the investigational product.

The study treatment phase is defined as the period between the date of first administration of investigational product and the date of last administration of investigational product + 30 days.

No replacement of missing values is planned, other than those noted in Section 6.2. Thus the number of patients included in the analyses may vary depending on availability of the parameter considered.

Descriptive statistics will be provided by dose level (DL1 to DL5 or DL6 then expansion cohort, depending on the disease cohort) and overall for each of the two patient cohorts (AL and OHM), and by time point when appropriate, according to the nature of the variable.

- For quantitative variables, descriptive statistics will include: number of missing values, number of observed values, minimum, maximum and median or mean and standard deviation.

- For qualitative variables, descriptive statistics will include: number and percentage of missing values, number of observed values, frequencies and percentages (only for the overall column) per modality.

Calculated statistics and percentages will be displayed with one decimal, unless otherwise specified.

No statistical tests will be performed due to the descriptive nature of this analysis.

In terms of terminology, the mention of "by dose level and overall" will always correspond to the following, according to the cohort:

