# 8.1 DATA SETS ANALYZED

Statistical analyses will be carried out as described below. The number of patients per analysis set will be tabulated by DL and overall according to the population evaluated.

A listing will also be provided (for CSR appendices).

The following table describes use of the above-defined patients populations in the different analyses conducted.

Analyses Sets	Enrolled	Safety	Evaluable for efficacy population	Evaluable for DLT
Disposition	×			
Population characteristics		$\checkmark$		
Compliance and exposure		$\checkmark$		
Efficacy assessments			✓	
DLT				✓
Safety assessment		$\checkmark$		

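### Compliance is computed only for patients with a gap-free dosing record, so longer-treated patients drop out more often; the resulting selection bias has unknown size and direction

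*SAP*

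**What the plan says.** - **Who gets a value.** SAP 10.5: "Compliance to the study treatment will be derived only for patients with no missing data (collected in the CRF").
- **The ratio.** Non-zero doses over completed CRF lines plus one: "nb dose not equal to 0 in the CRF / ( (nb completed lines in the CRF + 1" ), times 100.
- **The periods.** "Compliance over the whole study treatment period (from first visit to last visit) and over cycle 1 only will be calculated". The SAP does not say whether completeness is judged within each period or over all treatment.
- **The population.** The row "Compliance and exposure" in the SAP 8.1 table is ticked for the Safety set, defined in SAP 8 as everyone who received at least one dose.
- **Missing data in general.** SAP 6.1: "No replacement of missing values is planned, other than those noted in Section 6.2". The SAP 6.2 rules concern dates only. SAP 6.1 also lets the number analysed vary with availability, and asks for counts of missing and observed values for quantitative variables.
- **The record.** Protocol 5.2.3: "Details of the exact dose and time of administration of medication (day/month/year, h: min) will be documented" in a patient diary and reported in the CRF. Under Protocol 5.8, doses on non-visit days are taken at home and noted by the patient.
- **The aim.** The SAP synopsis says the expansion part is "to confirm feasibility, safety, PK and PD at the RD".

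**The concern.** The rule works at patient level: a record with one gap is discarded whole, however complete the rest of it is. With many intakes per patient, more intakes mean more chances of a gap. Retention therefore depends on how long, and on which schedule, a patient was treated. The figure then describes a selected part of the Safety set, and the selection differs between columns.

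At stake is the reading of a descriptive figure. Compliance helps to show whether the regimen could be taken as planned, which bears on the feasibility aim of the expansion part. Columns are small: 3 to 8 patients in escalation and 16 to 19 in expansion (SAP 6.1), so losing a few patients changes what a column represents.

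**Working it through.** **No plan figure to reproduce.** The documents give no expected compliance, no missing-record rate, and nothing on whether missing records go with missed doses. Those inputs are assumptions below.

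**Inputs from the documents.** 14 dosing days per 21-day cycle on the intermittent schedule and 21 on the continuous one. Column sizes from SAP 6.1 sum to 80 + 61 = 141.
- Started on a 21-21 schedule: AL 3 + 6, OHM 5 + 3 + 4 + 7 + 6 + 7, total 41.
- Expansion: 19 + 16 + 16 = 51, all on 80 mg QD 14-21.

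**Step 1: exclusion.** Assume one CRF record per intake, each missing independently with probability p. Then P(excluded) = 1 − (1 − p)^n for n records. The last two columns are six cycles of 14 and of 21 daily doses.

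| p | n = 14 | n = 21 | n = 84 | n = 126 |
|---|---|---|---|---|
| 0.1% | 1.4% | 2.1% | 8.1% | 11.8% |
| 0.5% | 6.8% | 10.0% | 34.4% | 46.8% |
| 1% | 13.1% | 19.0% | 57.0% | 71.8% |
| 2% | 24.6% | 34.6% | 81.7% | 92.2% |

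Example: if all 16 DLBCL expansion patients had 84 records, 16 × 0.57 ≈ 9 would have no whole-period value at p = 1%.

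**Step 2: what one gap costs in information.** Counting a single missing record as taken or as not taken moves that patient's compliance by 1/n: 1/14 = 7.1 points, 1/84 = 1.2 points, 1/126 = 0.8 points. The patients most likely to be discarded are those for whom one gap matters least.

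**Step 3: direction.** Take two equal groups with true compliance 98% and 90%, so the true mean is 94.0%. The complete-case mean weights each group by (1 − p)^n.
- Poorer compliers lose more records (p = 3% against 0.5%): 94.7% at n = 14 and 97.2% at n = 84, a bias of +0.7 and +3.2 points.
- Equal p: no bias.
- Better compliers lose more records (rates swapped): −0.7 and −3.2 points.

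Duration alone, with half the patients at 14 records and half at 84, and p = 1% throughout:
- Longer-treated patients comply less (92% against 96%): +0.7 points.
- Longer-treated patients comply better: −0.7 points.
- Equal compliance: 0.

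**Step 4: the added 1 in the denominator.** If every intake is a completed line, a perfect patient scores n/(n + 1): 14/15 = 93.3%, 84/85 = 98.8%. With true compliance 94% in both duration groups, the ratio gives 0.94 × 14/15 = 87.7% and 0.94 × 84/85 = 92.9%, mean 90.3%. At p = 1% the complete-case mean falls to 89.4%. Here, losing longer-treated patients lowers the reported figure.

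**The case against.** **Availability-limited numbers are the SAP's convention.** SAP 6.1 allows them and already asks for missing and observed counts per column, so a reader would see how many patients lack a value. This stands, and it reduces the mismatch with SAP 8.1 to a gap between the assigned set and the patients actually described. It does not justify treating a nearly complete record as unavailable, and a patient count does not show how few days were missing.

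**A blank diary day is not necessarily a blank CRF line.** Staff document intake on visit days, nurse's notes can serve as source (Protocol 5.8), CRFs are checked against source (13.1), and missing data must be explained (14.1). This stands too. The true rate may be low, and at 0.1% the effect is small. The SAP also leaves the CRF line undefined, so one record per intake is an inference from Protocol 5.2.3.

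**Other measures of dose delivery exist.** SAP 12.2 reports relative dose intensity, reductions, interruptions and delays with no complete-record restriction. No passage names compliance as the measure of feasibility, so a reader should not infer that the feasibility conclusion rests on it.

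**Stronger readings the documents do not support.** A reader might infer that the rule removes careless patients and so inflates compliance. Nothing in the documents links gaps to missed doses, and Steps 3 and 4 give either sign. A reader might also carry the 14/21 against 21/21 contrast into the expansion part; all 51 expansion patients are on 14/21 once daily, so it does not apply there.

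**Conclusion.** The point holds in a limited form. SAP 10.5 is a patient-level complete-case rule applied to a set that SAP 8.1 defines as all treated patients. Given one CRF record per intake and independent gaps, exclusion rises with the number of records: 13%, 19%, 57% and 72% at 14, 21, 84 and 126 records if 1% are missing, and at most about 12% if 0.1% are. These percentages measure exclusion, not bias in compliance.

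The bias has unknown size and direction, and is upward only if missing records go with missed doses. In escalation, the selection differs by duration and by schedule (41 of the 141 patients started on 21-21). In expansion, only selection by treatment duration remains, and only for the whole-period figure if completeness is judged within each period. If a later gap also removes a patient from the cycle 1 figure, the duration effect reaches that figure too.

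DLT and the recommended dose are unaffected. This is a worthwhile, low-cost improvement, not a flaw in the trial's conclusions.

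**What to change.** Amend SAP 10.5 as follows:

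1. Derive compliance for all treated patients, with scheduled dosing days as the denominator. This also replaces the unexplained added 1.
2. Judge completeness separately for cycle 1 and for the whole period.
3. Report a range: missing records counted as not taken (lower bound) and as taken (upper bound), or left out. Keep the complete-case figure as a sensitivity analysis.
4. Print the number of missing dosing days per column beside the missing-patient count that SAP 6.1 already requires.
5. Use returned-capsule counts to resolve gaps only if they are in the database. The synopsis says pharmacists "retrieve the unused capsules that will be kept until study end for accountability by the study monitor", which does not show that the counts were entered for analysis; they also give totals per visit interval, not days.

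Cost: SAP wording and slightly more programming on CRF data. SAP 16.1 already allows the presented data to change during programming by agreement. The downside is that the lower bound may look less favourable than a complete-case figure.

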# 11. EFFICACY ANALYSES

Response: tumor response will be assessed throughout the study according to standard criteria; acute leukemia patients will be assessed based on the recommendations from the European LeukemiaNet [*Döhner 2010*], lymphoma patients according to [*Cheson 2007*], and MM patients according to [*Durie 2006*].

Tumor response will be tabulated per DL and overall, according to disease indication (AL/lymphoma/MM) in evaluable patients.

Waterfall plots showing disease response according to DL will be prepared for lymphoma patients according to tumor dimensions, and for AL patients in terms of percent peripheral blood blasts decrease, percent BM blasts decrease and percent neutrophil increase (with different colors per dose level).

A listing of all responders will be provided including response, disease indication, duration of response.

Duration of response is defined as the time from the date of response to the date of documented progression or death. If progression or death is not observed during the study, data will be censored at the last date of documented response.

Event	Censoring decision	Event or censored date
PD during the study	Not censored	Date of last assessment
Lost to follow-up	Censored	Date of last assessment
Study ended without PD or death	Censored	Date of last assessment
Death during the study	Not censored	Date of death

Patients with any possible evidence of antitumor activity will be reported and described with narratives: standard responses (all patients), minor tumor shrinkages (lymphomas), neutrophil increase, platelets increase, transfusion requirement decrease, no further requirement of hydroxyurea, partial blasts clearance (AL patients), unexpected long stabilization (all patients).

# **12. SAFETY EVALUATION**

# **12.1** SAFETY VARIABLES

Safety analyses will be performed in the Safety Population other than for DLT which will be presented in the evaluable for DLT population. All safety data from the study treatment phase will be presented.

Safety data are obtained from clinical and physical examinations, as well as vital signs evaluation.

TEAEs / signs and symptoms of disease observed by the investigator (preferably by the same physician for the same patient) or reported by patients to the study nurses will be recorded and graded according to NCI-CTCAE version 4.03.

Clinically significant laboratory results are those which have clinical consequences. The seriousness, the action taken regarding study medication and patient participation in the study, relation to study medication and the most likely cause, should then be recorded.

# **12.2 TREATMENT EXPOSURE**

OTX015/MK-8628 treatment will be described by DL and overall.

The intended dose (mg, mg/kg, mg/m^2), study duration (days), treatment duration (days), number cycles initiated, cumulative dose (mg), absolute dose intensity (mg/week), the relative dose intensity (%).

In addition, treatment modifications will be described including, the number (%) of patients having at least one dose reduction (compared to the initial DL), intra-cycle interruption (dose 0 between two non 0 doses),

delay (definition), or dose increase (compared to the initial DL). The number of modifications per patient and per modification type will be reported and listings will be provided.

- Intended dose (mg,  $mg/m^2$ , mg/kg) = nb of planned courses \* planned dose by course
- Study duration =[(last cycle dose date first cycle dose date)/7 + 1]
- N days treatment intake (observed) =
- Actual cumulative dose (mg) = sum of all doses received from first cycle 1 day 1 to actual last day of treatment during the last cycle
- Absolute dose intensity (mg/week) = Actual cumulative dose / Actual duration
- Relative dose intensity (%)=[Actual dose intensity / Planned dose intensity]\*100
- Cumulative dose during the cycle 1  $(mg/m^2)$  = sum of all doses received during cycle 1 with
- Planned period of administration = 21 days

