- Dose escalation guidelines are detailed in section 3.1.1. The dose escalation will proceed following the same rule in two separate subsets of patients (i.e. AL or other hematological malignancies)
- Enrolled patients will take OTX015/MK-8628 at the DL they were assigned at study entry throughout the study, or at reduced dose according to toxicity encountered (see 0).
- Intrapatient dose escalation: In exceptional circumstances, intra-patient dose escalation could be allowed, provided all the following conditions are met: 1) The patient did not experienced toxicity of grade > 1 while treated at the initial dose for at least 2 cycles; 2) The dose immediately above has already been tested and is considered safe (i.e. at least 3 patients were treated over 3 weeks and no DLT was observed, or at least 6 were treated over 3 weeks and no more than one of them has experienced a DLT); 3) the patient has experienced stable disease so far (no response and no progression); 4) the investigator considers the patient could benefit from dose increment and 5) the SMC agrees.

The recommended dose (RD) for expansion cohorts for both acute leukemia and other hematologic malignancies is 80mg QD days 1 to 14 of 21-day cycles (2 weeks ON/one week OFF).

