### Treatment

- Patients should receive the study treatment within 7 days after registration.
- All patients will be hospitalized for at least 8 hours after the first study drug administration to check vital signs and ECG and collect PK blood samples around the anticipated Tmax.
- Patients will take OTX015/MK-8628 orally, daily in a fasted state just before lunch, at least 3 hours after breakfast end (except outpatient who must take the study medication before breakfast at the hospital on day 1). The schedule of administration will initially depend on the indication:

- AL patients will initially take OTX015/MK-8628, over 14 consecutive days followed by a 7day rest period. Upon SMC decision, AL patients may take OTX015/MK-8628 continuously without planned rest period (as for OHM patients).

- OHM patients will take OTX015/MK-8628 continuously without planned rest period
- a cycle = 21 days by convention.
- The initial daily schedule of administration will be once a day (QD) at the first DL. Based upon PK and PD results, this schedule could be modified (e.g. to twice daily [BID] by SMC decision) for further patients. For the BID schedule, patients will take their medication in a fasted state around 8 a.m. (± 2 hours) and 8 p.m. (± 2 hours).
- Treatment will be interrupted in cases of toxicity according to specific guidelines (see dose and schedule adaptation).
- Enrolled patients will receive OTX015/MK-8628 at the DL they were assigned at study entry throughout the study, or at reduced dose according to toxicity encountered.
- However, in exceptional circumstances, intra-patient dose escalation could be allowed, provided all the following conditions are met: 1) The patient did not experience toxicity of grade > 1 while treated at the initial dose for at least 2 cycles; 2) The dose immediately above has already been tested and is considered safe (i.e. at least 3 patients were treated over 3 weeks and no DLT was observed, or at least 6 were treated over 3 weeks and no more than one of them has experienced a DLT); 3) the patient has experienced stable disease so far (no response and no progression); 4) the investigator considers that the patient could benefit from dose increment and 5) the SMC agrees.

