### **Other Hematologic Malignancies Patients**

			DL4A	DL4B	DL5A	DL5B	DL5C	DL5D	Exp. (80mg	
DL1 (10mg	DL2 (20mg	DL3 (40mg	(80mg QD)	(40mg BID)	(120mg QD)	(120mg QD)	(120mg QD)	(120mg QD)	QD) 14-21 -	
QD) 21-21	QD) 21-21	QD) 21-21	21-21	21-21	21-21	14-21	5-7	7-21	DLBCL	Total
(N=5)	(N=3)	(N=4)	(N=7)	(N=6)	(N=7)	(N=3)	(N=5)	(N=5)	(N=16)	(N=61)

All analyses will be repeated in the two populations, AL patients and OHM patients, unless otherwise specified.

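### The SAP 12.2 interruption rule misses any hold that runs to the last planned dosing day of a cycle, and delay, the category that might catch it, is left undefined

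*SAP*

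**What the plan says.** SAP 12.2 lists the treatment modifications to be described: dose reduction, interruption, delay and dose increase. Interruption is an "intra-cycle interruption (dose 0 between two non 0 doses". The next item reads "delay (definition), or dose increase (compared to the initial DL", so the definition of delay was never filled in. Neither entry mentions planned dosing days or planned rest days.

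The SAP synopsis (Treatment) fixes the cycle for every schedule: "a cycle = 21 days by convention". SAP 12.2 repeats that length for exposure: "Planned period of administration = 21 days". The expansion dose is "80 mg QD days 1 to 14 of 21-day cycles (2 weeks ON/one week OFF", and Protocol 5.2.4.1 agrees ("80mg QD days 1 to 14 of 21-day cycles (2 weeks ON/one week OFF"). The column headers in SAP 6.1 also include continuous (21-21), 7-21 and 5-7 groups. For the later OHM columns they read "14-21 5-7 7-21 DLBCL Total" with sizes "N=3) (N=5) (N=5) (N=16) (N=61".

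Table ii-2 (SAP appendix, Exposure) reports the number of patients with at least one interruption and the number per patient. Listing ii-1 gives the reasons. Both use the terms without defining them again.

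**The concern.** The rule needs a non-zero dose after the hold and within the same cycle. On an intermittent schedule the rest period closes the cycle, so a hold that reaches it fails the test by construction. A short hold with a quick restart is counted, while a longer one that does not recover in time is not. Routine cycle 1 visits fall on days 8, 15 and 22 (Protocol flow chart). On 14-21, a hold begun on day 8 must therefore resolve and restart within the six remaining dosing days, 9 to 14, to be counted at all.

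The expansion part is there to confirm feasibility and safety at the recommended dose. SAP 6.1 plans no statistical tests, so the descriptive tables are the evidence. An interruption rate at the recommended dose that leaves out a defined class of holds may look more favourable than the dosing record supports.

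**Working it through.** The plan states no figure that depends on this rule, so the check applies the rule as written to day-by-day dosing in a 21-day cycle.

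**Who is on which schedule (SAP 6.1 headers).**
- AL on 14-21: 3+3+4+4+8+7+7+19+16 = 71. AL on 21-21: 3+6 = 9. Total 80.
- OHM on 21-21: 5+3+4+7+6+7 = 32. On 14-21: 3+16 = 19. On 5-7: 5. On 7-21: 5. Total 61.
- 80+61 = 141, which matches SAP 7.
- 14-21 and 7-21 together: 71+19+5 = 95, and 95/141 = 67%. Expansion patients, all on 14-21: 19+16+16 = 51.

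**Rule applied literally.** A run of zero doses counts only if a non-zero dose precedes and follows it in the same cycle.

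| Schedule | Hold on days | Planned doses missed | Later dose in the cycle? | Counted? |
|---|---|---|---|---|
| 14-21 | 10-12 | 3 of 14 | yes | yes |
| 14-21 | 10-14 | 5 of 14 | no | no |
| 14-21 | 8-14 | 7 of 14 | no | no |
| 14-21 | 4-14 | 11 of 14 | no | no |
| 7-21 | 4-6 | 3 of 7 | yes | yes |
| 7-21 | 4-7 | 4 of 7 | no | no |
| 21-21 | 10-14 | 5 of 21 | yes | yes |
| 21-21 | 10-21 | 12 of 21 | no | no |

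On 14-21 there are 13+12+...+1 = 91 possible single holds that start on day 2 or later and end by day 14. The 13 that end on day 14 are not counted. This is an enumeration of patterns, not a probability.

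**Would delay catch them?** With a hold on days 10-14 and cycle 2 starting on day 22 as planned, no cycle has started late. Under the ordinary meaning of the word there is no delay, and the SAP supplies no other meaning. On 7-21 the rest period gives the same room. On 21-21 there is no rest period to absorb recovery, so an on-time next cycle requires dosing to resume exactly at the cycle boundary.

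**Reading the rule across cycles.** If the restriction to one cycle is dropped, these holds are caught when dosing resumes. But any planned rest week recorded as dose 0 is then counted as well.

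**The 5-7 group (N=5), conditional.** Assume 5 days on and 2 off: doses fall on days 1-5, 8-12 and 15-19, which is 15 doses. Rest days 6-7 and 13-14 lie between doses; days 20-21 do not. If rest days are entered as dose 0, a fully compliant cycle shows 2 interruptions. If they have no CRF line, it shows none.

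**Counting against planned dosing days instead.** The 14-21 hold on days 10-14 becomes one interruption with 5 planned doses missed, and a compliant 5-7 cycle gives 0.

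**The case against.** The best reply is that little is lost from the report as a whole, and much of it stands.

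- **Reductions.** Under the dose adaptation rules in both documents, dosing resumes after a qualifying toxicity at a reduced dose. Such a patient appears under reductions in the same Table ii-2 and, for AEs, in Listing ii-2. Holds resumed at the same dose do not.
- **Discontinuations.** Holds that end treatment appear in Tables i-4 and iv-2 and Listings i-4 and iv-1.
- **Cycle 1.** Missing 3 of 14 doses gives 11/14 = 78.6%, below the 85% threshold in SAP 8. The patient then either has a DLT or is listed as not evaluable with a reason. This route does not exist in later cycles.
- **Delay.** The word may have been meant broadly. Table i-4 speaks of a treatment delay of over two weeks for toxicity where the synopsis calls the same thing an interruption. That is possible, but a blank definition cannot be programmed on a guess.

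A reader might also infer several stronger things that the documents do not support.

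- **That the most serious holds vanish from the report.** They are missing from the interruption count, not from the tables and listings above.
- **That 100 of 141 patients are miscounted.** That figure (90+5+5) is the number on schedules with rest days, and it pools missed holds with the possible false positives on 5-7.
- **That 14-21 is bound to look better than 21-21.** A hold from day 10 that could restart on day 17 is counted on 21-21 and missed on 14-21, so a distortion is possible. But holds reaching day 21 on 21-21 (41 patients) are missed too, and nothing in the documents gives the net effect.
- **That compliant 5-7 patients are certainly counted as interrupted.** The documents neither spell out 5-7 nor say how rest days are recorded. The compliance formula in SAP 10.5 hints against zero-dose lines: with them, a fully compliant 14-21 cycle would score 14/(21+1) = 64%. That is inference, not proof.

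**Conclusion.** The point holds as a defect in one stated rule. Applied literally, SAP 12.2 leaves out of the interruption count every hold that reaches the last planned dosing day of a cycle, and no defined category picks it up. The gap matters most on 14-21 and 7-21, because there the rest period lets the next cycle start on time.

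The 95 patients are those exposed to the rule on these two schedules. How many had such a hold cannot be known from the documents. The error is confined to the descriptive interruption counts in Table ii-2 and the related listing; DLT determination and cumulative dose do not use the rule. The conclusion assumes that the restriction to one cycle is meant as written and that delay carries its ordinary meaning. The 5-7 false positives rest on two further assumptions: 5 days on and 2 off, and rest days recorded as dose 0.

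**What to change.** In SAP 12.2:

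- Define an interruption as one or more consecutive planned dosing days with dose 0, excluding planned rest days for the patient's schedule, whether or not dosing resumes in that cycle.
- Show holds that end in permanent discontinuation on a separate line, so that they are neither lost nor mixed with temporary holds.
- Report patients affected, planned doses missed, and the subset due to AEs.
- Define delay as the next cycle starting after its planned day 1.

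The cost is SAP wording and reprogramming of Table ii-2 and Listing ii-1, from dosing data already collected. The SAP appendix (16.1) already allows output changes during programming. The interruption rate at the recommended dose may look less favourable.
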